### 7.2.6. Asthma Exacerbation Stopping Criteria (Part C Only)

Any participant experiencing an exacerbation of asthma must be withdrawn from the study. An asthma exacerbation is defined as follows:

- Episodes characterised by a progressive increase in symptoms of shortness of breath, cough, wheezing or chest tightness and progressive decrease in lung function, i.e. they represent a change from the patient's usual status that is sufficient to require a change in treatment [[GINA](#), 2020].
- A progressive decrease in lung function is defined as sustained drop in PEF of > 20 % from baseline (Day 1, predose) maintained for  $\geq 3$  days. In the absence of PEF measurements, Investigator judgement will be applied.

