**Footnotes to Part C: Repeat Dose | Asthma (Cohort 5)**

1. Day -1 inhaler training may be performed on Day 1 if needed and before administration of the first dose. Additional training may be provided as needed and according to Investigator discretion.
2. To be performed according to local site procedures. Additional ad hoc testing may be implemented based on local site procedures.
3. Predose and 30 min only.
4. PEF measurements will be taken in triplicate twice each day (once in morning upon waking and once in the evening before bedtime) from Day -1 evening until discharge on Day 8. Clinical site staff will complete and record the PEF measurements at each time point.
5. Provide PEF device refresher training if necessary.
6. Includes systolic and diastolic blood pressure, heart rate, respiration rate and tympanic temperature.
7. Predose only
8. On treatment days ECGs will be collected at predose and 6-hours post-dose. On Day 1 predose, triplicate measurements will be collected, and the mean values will be used to calculate baseline. At all other times single ECGs can be taken.
9. Cardiac telemetry to start approximately 1-hour pre-dose and continuously until 6 hours post dose.
10. Clinical Chemistry and Haematology only.
11. At pre-dose, 5 min, 15 min, 30 min, 45 min, 1 h, 2 h, 4 h, 6 h, 8 h, 12 h and 16 h

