##### TYPE OF PARTICIPANT

2. Participants who are otherwise healthy (other than the acceptable condition of asthma and other mild atopic diseases, including allergic rhinitis and atopic dermatitis) as determined by medical evaluation based on screening medical history, physical examination, vital signs, ECG assessment, pulmonary function testing, laboratory tests and cardiac monitoring.
  - **Note:** A participant with a clinical abnormality or laboratory parameter(s) not specifically listed in the exclusion or exclusion criteria that is outside the reference range for the population being studied may be included only if the investigator, in consultation with the Medical Monitor (if required), agree and document that the finding is unlikely to introduce additional risk factors and will not interfere with the study procedures.
3. A current confirmed physician diagnosis of asthma (as defined by the British Thoracic Society/ Scottish Intercollegiate Guidelines Network ([BTS/SIGN](#), 2019), or the Global Initiative for Asthma ([GINA](#), 2020 guidelines)) at least 6 months before screening. The reason for diagnosis of asthma should be documented in the participant's source data, including relevant history.

4. A screening pre-bronchodilator FEV1  $\geq$  65% predicted normal value.  
**Note:** Predicted values based on European Respiratory Society (ERS) guidelines [Quanjer, 2012].

5. Participants with maintained control of their asthma using the permitted medications listed below, will be recruited as follows:

Permitted Medication Use	Number of Participants
SABA use and/or intermittent ICS/LABA use.	n=8
Regular treatment with ICS or ICS/LABA (including use of Leukotriene Receptor Agonist (LTRA))	n=8

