### 5.3. Lifestyle Considerations

#### 5.3.1. Meals and Dietary Restrictions

- Refrain from consumption of Seville oranges, grapefruit or grapefruit juice, pomelos, exotic citrus fruits, grapefruit hybrids from 7 days before the start of study intervention until discharge from the unit.

- No water is allowed until 2 hours after dosing, water is allowed ad libitum at all other times.
- Participants must fast overnight until 2 hours after each dose.

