### **6.7.1.      Rescue Medicine**

For asthmatics in Part C of this study SABA (e.g. salbutamol) will be permitted to be used as rescue medication. This will be provided by the participant or, if necessary, supplied by the study site.

The use of rescue medications is allowable and at any time during the study. The date and time of rescue medication administration as well as the name and dosage regimen of the rescue medication must be recorded.

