## 8. STUDY ASSESSMENTS AND PROCEDURES

- Study procedures and their timing are summarized in the SoA.
- Protocol waivers or exemptions are not allowed.
- Immediate safety concerns should be discussed with the Sponsor immediately upon occurrence or awareness to determine if the participant should continue or discontinue study intervention.
- Adherence to the study design requirements, including those specified in the SoA, is essential and required for study conduct.
- All screening evaluations must be completed and reviewed to confirm that potential participants meet all eligibility criteria. The Investigator will maintain a screening log to record details of all participants screened and to confirm eligibility or record reasons for screening failure, as applicable.
- Procedures conducted as part of the participant's routine clinical management (e.g., blood count) and obtained before signing of ICF may be utilized for screening or baseline purposes provided the procedure met the protocol-specified criteria and was performed within the time frame defined in the SoA.
- Individual PK data that could unblind the study will not be reported to investigative sites or other blinded personnel until the study has been unblinded. The maximum amount of blood collected from each participant over the duration of the study, including any extra assessments that may be required, will not exceed 500 mL.

Repeat or unscheduled samples may be taken for safety reasons or for technical issues with the samples. Additional considerations around Covid-19 can be found in [Appendix 8](#).

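### Part C: the mandatory exacerbation withdrawal rule (Protocol 7.2.6) misses a symptomatic deterioration that needs a treatment change but reverses in under three days

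*Protocol*

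**What the plan says.** Protocol 7.2.6 applies to Part C only and requires withdrawal of any participant with an exacerbation. The definition joins a progressive rise in symptoms to a progressive fall in lung function with the word and. It then explains such episodes: "they represent a change from the patient's usual status that is sufficient to require a change in treatment".

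The footnote fixes the lung-function element: a "progressive decrease in lung function is defined as sustained drop in PEF of > 20 % from baseline (Day 1, predose) maintained for" three days or more. There is one exception: "In the absence of PEF measurements, Investigator judgement will be applied".

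PEF will normally be present. Footnote 4 to the Part C Schedule of Activities has site staff record triplicate values "twice each day (once in morning upon waking and once in the evening before bedtime) from Day -1 evening until discharge on Day 8". Dosing lasts 7 days (Protocol 4.1).

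**The concern.** An asthma exacerbation is the event that this rule exists to catch, and the rule is mandatory so that withdrawal does not rest on case-by-case judgement. Read literally, the two parts of the definition pull apart. A participant whose symptoms worsen, whose PEF falls by more than 20%, who is given new treatment and who recovers within two days fits the rule's own description of an exacerbation but fails its PEF duration test. Effective treatment can itself end the fall before the test is met.

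At stake is whether withdrawal after such an episode follows from the rule or from discretion. The bar on restarting in Protocol 7.2.8 is also tied to stopping criteria having been met, so it does not clearly apply to an episode that falls short of them. No planned analysis in the SAP depends on 7.2.6; this is a safety-conduct point.

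**Working it through.** The plan states no figure on this point, so there is none to reproduce. The check has two parts.

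**Logic of the rule**

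1. Symptoms and lung-function decline are joined by and, so both are needed.
2. The footnote defines the decline, so with PEF available the sustained fall of more than 20% is necessary.
3. The treatment-change wording follows i.e. It describes the episode and is not written as an alternative trigger.
4. The exception needs PEF to be absent. Twice-daily recording by staff makes that rare.
5. Hence a treatment-changing episode with PEF recovering in under three days does not meet 7.2.6.

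**How long a fall can last without meeting the rule**

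Assumption: each dose is given in the morning after the waking PEF. The documents do not state the clock time. The assumption rests on the overnight fast ("Participants must fast overnight until 2 hours after each dose", Protocol 5.3.1) and the Day 1 predose baseline. The protocol does not say how three days is counted, so both readings are shown for a fall first seen on Day d.

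- *Calendar days.* The rule is met at the Day d+2 morning reading.
  - Morning onset: d am, d pm, d+1 am, d+1 pm, d+2 am = 5 low readings, so 4 can pass without a trigger. Doses given meanwhile: Days d and d+1 = 2.
  - Evening onset: d pm, d+1 am, d+1 pm, d+2 am = 4 low readings, so 3 can pass. Doses meanwhile: Day d+1 = 1.
- *72 hours.* The rule is met at the same time of day on Day d+3. That takes 3 × 2 + 1 = 7 low readings, so 6 can pass. Doses meanwhile = 3.

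Sensitivity: if the calendar rule is met only at the third day's evening reading, 5 to 6 low readings are needed and 2 to 3 doses are given first. If 72 hours is read as six consecutive readings, 2 to 3 doses are given first.

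**Persistent falls (context only)**

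Post-baseline readings: Day 1 evening, Days 2 to 7 twice daily, Day 8 morning = 1 + 12 + 1 = 14. A dose is still to come after those from Day 1 evening to Day 7 morning = 1 + 10 + 1 = 12.

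- A fall that persists from onset spares at least one dose at 1 + 8 = 9 of the 12 onsets (calendar, d ≤ 5), or 6 of 12 (72 hours, Day 1 evening to Day 4 morning).
- It cannot meet the rule by Day 8 morning at 1 of 12 (calendar, Day 7 morning), or 4 of 12 (72 hours, Day 5 evening to Day 7 morning).

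These are schedule slots for falls that do not reverse. They show why the undefined day count matters in a 7-day course; they do not measure the gap for short episodes.

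**The case against.** The strongest answer is that few participants would be left unprotected.

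- Bronchospasm already means immediate discontinuation and withdrawal (2.3.1), and many short episodes with wheeze would fall there, although bronchospasm is not defined.
- Participants are inpatients from Day -1 to Day 8 and are dosed under medical supervision (6.4).
- The investigator may withdraw anyone for safety (7.3), and Section 8 adds: "Immediate safety concerns should be discussed with the Sponsor immediately upon occurrence or awareness".
- A worsening of a pre-existing condition can be an AE (10.3.1), and related severe events feed the pause and dose-stopping rules (7.2.1, 6.5.2).
- An investigator could also read the treatment-change clause as sufficient on its own.

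Most of this stands, and it keeps the point small. It does not remove it. Discretion is what a mandatory rule is meant to replace, and a clause open to two readings in such a rule is itself a reason to amend it.

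One apparent protection is weaker than it looks. Section 7.2.5 acts on FEV1 at 1 hour post-dose against the same day's predose value, while Part C dosing-day spirometry is scheduled only at predose and 30 minutes. It should not be counted as a firm backstop.

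Three stronger readings are tempting but unsupported.

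- A reader might infer that such a participant has to stay on drug. The other withdrawal routes show otherwise.
- A reader might infer that new or increased ICS or ICS/LABA escapes consultation altogether because Section 6.7 lists these as permitted. That permission depends on asthma severity, and the note to Part C exclusion 9 mentions only low-dose ICS/LABA, so some escalations plausibly need the Medical Monitor's opinion.
- A reader might take the persistent-fall slot counts as the benefit of a fix. A persistent symptomatic fall without a treatment change would wait just as long after the amendment below.

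**Conclusion.** The point holds as a low-cost improvement to one safety rule. Whenever PEF is measured, 7.2.6 does not capture a treatment-changing symptomatic deterioration that reverses in under three days, although its own wording describes one.

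This rests on reading the footnote as a necessary condition, which is its plain sense. The reading counts (up to 3 or 4 consecutive low readings by calendar days, 6 by 72 hours) also rest on the assumed morning dosing. They are not risks: the documents give no exacerbation rate, and Part C has 16 participants, 12 on active. The practical gain is small, because bronchospasm withdrawal, inpatient supervision and discretion remain. The documents do not support calling Part C unsafe.

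**What to change.** Amend Protocol 7.2.6 in three respects.

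1. Make a progressive increase in asthma symptoms that requires treatment beyond as-needed SABA and the participant's existing regimen sufficient for withdrawal, however long the PEF fall lasts. Examples are systemic corticosteroid, or new or increased regular ICS or ICS/LABA. As-needed SABA is left out because Section 6.7.1 already allows it: "The use of rescue medications is allowable and at any time during the study". In the stratum defined by "SABA use and/or intermittent ICS/LABA use", as-needed use of the participant's own ICS/LABA counts as existing regimen, and starting regular use counts as a change.
2. Keep worsening symptoms plus a sustained PEF fall of more than 20% as a second trigger. Say that symptoms are still required, so that an isolated PEF fall does not newly force withdrawal.
3. State whether three days means calendar days or 72 hours.

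Cost: an amendment with ethics approval (10.1.1), and health-authority approval if it is substantial. No new measurement is needed. Slightly more of the 16 Part C participants might be withdrawn; they may be replaced under 7.3. Deciding that symptoms require new treatment remains a clinical judgement, but withdrawal would then follow from it.

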### 7.2.7. Temporary Discontinuation

Participant withdrawn from the study treatment will be withdrawn from the study.

### 7.2.8. Rechallenge

Study intervention restart or rechallenge after stopping criteria are met by any participant in this study is not allowed.

## 7.3. Participant Discontinuation/Withdrawal from the Study

- A participant may withdraw from the study at any time at his/her own request or may be withdrawn at any time at the discretion of the investigator for safety, behavioural, or compliance reasons. This is expected to be uncommon.
- At the time of discontinuing from the study, if possible, the procedures outlined in the SOA on the day of discharge from the clinical unit should be completed (i.e. Days 2, 3, 18 and 8 for Parts A Cohort 1, A Cohort 2, B and C respectively).
- The participant will be permanently discontinued both from the study intervention and from the study at that time.
- If the participant withdraws consent for disclosure of future information, the Sponsor may retain and continue to use any data collected before such a withdrawal of consent.
- If a participant withdraws from the study, he/she may request destruction of any samples taken and not tested, and the Investigator must document this in the site study records.
- If participants prematurely discontinue in the study, they may be replaced at the discretion of the Medical Monitor in consultation with the Principal Investigator.

In Part A, the replacement participant will be assigned to the same treatment sequence and may start the treatment period where the last participant prematurely discontinued. In Parts B and C participants will be assigned to same treatment as the participant prematurely discontinued.

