**Brief Summary:**

For Part A, sufficient healthy adult participants will be screened to ensure a total of 24 participants are randomised in Cohorts 1 and 2 with the aim to achieve approximately 24 completed. Cohorts 1 and 2 will each consist of 12 healthy participants receiving study intervention in treatment periods 1 to 3 and 4 to 6 (9 active and 3 placebo per period), respectively.

In Part B, sufficient healthy adult participants will be screened to ensure 8 healthy participants are randomised to each of the two cohorts, with the aim to achieve approximately 8 completed in each cohort. A total of 16 healthy participants will be randomised in Part B to achieve 16 completers, 12 on active and 4 on placebo (6 active and 2 placebo in each of Cohorts 3 and 4).

For Part C, sufficient participants with asthma will be screened to ensure 16 participants are randomised, with the aim to achieve 16 completers, 12 on active and 4 on placebo.

If participants prematurely discontinue the study, they will be replaced at the discretion of the sponsor Medical Monitor in consultation with the Principal Investigator. In Part A, the replacement participant will be assigned to the same treatment sequence and may start the treatment period where the last participant prematurely discontinued. In Parts B and C participants will be assigned to same treatment as the last participant prematurely discontinued.

Each participant may only be randomised to one cohort and may only participate in one part of the study.

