#### **Part C: Repeat Dose in Participants with Asthma (Parallel Group)**

In Part C, further repeat dosing of GSK3923868 for 7 days will be assessed in a single parallel cohort (Cohort 5) of 16 participants with stable asthma. The dose for Part C will be based on the review of safety, tolerability and plasma PK data in Part B up to Day 14, 24 hours (from a minimum of 10 participants on active treatment). The dose level in Part C will not exceed the dose used in Part B. **cci**

Participants in Part C will be recruited based on their asthma severity, such that 8 participants will be mild or intermittent asthmatics requiring only treatment with short-acting beta agonist (SABA) and/or intermittent inhaled corticosteroid (ICS)/long-acting beta agonist (LABA) combination and 8 participants will have moderate asthma requiring regular treatment with ICS or ICS/LABA. Randomisation will be stratified to ensure 6 participants using intermittent SABA or intermittent ICS/LABA and 6 participants taking regular ICS or ICS/LABA will be on active treatment.

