## **6.3. Measures to Minimize Bias: Randomization and Blinding**

All participants will be randomized, according to the randomization schedule generated prior to the study by the Biostatistics Department at GSK. Each participant will be dispensed blinded study intervention, labelled with his/her unique randomisation number, throughout the study. Each participant scheduled to receive study drug will receive a treatment allocation number when randomized. In Part A (Cohorts 1 and 2), Part B (Cohorts 3 and 4) and Part C (Cohort 5) participants will be randomized in a 3:1 ratio to receive study treatment (active drug: placebo).

This will be a double-blind study with participants and the site staff blinded. The site pharmacy will be unblinded. For dose escalation, the Sponsor study team physicians, statisticians, clinical safety and clinical pharmacokinetic staff and/or their delegates will have access to unblinded data, if necessary. Other Sponsor staff will remain blinded unless unblinding becomes necessary.

Once each cohort is complete, selected members of the sponsor staff may have access to unblinded PK and safety data for the given cohort, to enable the PK analysis and modelling and to support the planning of future studies.

The blind may be broken if, in the opinion of the Investigator, it is in the participant's best interest for the investigator to know the study treatment assignment. The Sponsor study team must be notified before the blind is broken unless identification of the study treatment is required for a medical emergency in which the knowledge of the specific blinded study treatment will affect the immediate management of the participant's condition. In this case, the Sponsor study team must be notified within 24 hours after breaking the blind. The date and reason that the blind was broken must be recorded in the source documentation and eCRF, as applicable.

Unblinded monitors, and in the event of a Quality Assurance audit, the auditor(s), will be allowed access to un-blinded study treatment records at the site to verify that randomization/dispensing has been done accurately.

A participant will be withdrawn if the participant's treatment code is unblinded by the Investigator or treating physician. The primary reason for discontinuation (the event or condition which led to the unblinding) will be recorded in the eCRF.

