Study intervention Assignment	
In Part A (Cohorts 1 and 2), each cohort has a crossover design with four treatment sequences that participants will be randomized to. Of the four sequences, three include placebo for one of the treatment periods whilst the last contains active for all treatment periods. This gives a 3:1 active:placebo ratio within each treatment period of the cohort (as shown below):
																				

Overview of Study Design and Key Features

	Treatment Period	Cohort 1				Cohort 2			
		(n=3)	(n=3)	(n=3)	(n=3)	(n=3)	(n=3)	(n=3)	(n=3)
1	A	A	A	P			-		
2	P	A	A	A			-		
3	A	P	A	A			-		
4			-		P	A	A	A	
5			-		A	P	A	A	
6			-		A	A	P	A	

Part B (Cohorts 3 and 4), follow a parallel group design where participants will be randomized in a 3:1 ratio (active:placebo) to receive study treatment.

Part C (Cohort 5) also follows a parallel group design with participants randomized in a 3:1 ratio (active:placebo) to receive study treatment. In addition, Part C will be stratified to ensure 8 SABA and/or intermittent ICS/LABA participants (6 active and 2 placebo) and 8 ICS or ICS/LABA participants (6 active and 2 placebo) are randomized.

Interim Analysis	There are no formal interim analyses conducted as part of this study, however the following in-stream analyses will be performed as described in the sections below.
Dose Escalation Committee	A review of preliminary safety, tolerability and plasma PK data will be conducted by the DEC prior to each dose level in Part A, before initiating repeat dosing in Part B, and before initiating repeat dosing asthmatics in Part C. Safety and tolerability data includes adverse event/serious adverse event (AE/SAE), clinical laboratory values, 12-lead electrocardiogram (ECG), vital signs and spirometry measurements. Additional details are available in the Dose Escalation Plan.
Instream Analysis of PK Data	Once each of Part A (Cohorts 1 and 2) and Part B (Cohorts 3 and 4) have completed, selected members of the GSK team will be formally unblinded to the treatment allocations of the completed participants for PK and safety data from these cohorts to enable the analysis and modelling of PK data to start. The aim of this analysis is to inform internal decision making around dose selection for future studies in the development plan of this compound. This analysis will not impact the conduct or the design of the current study and will be reported separately from this SAP.

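### In Parts B and C, the replacement for a participant whose code the investigator has broken inherits a treatment that the investigator already knows

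*Protocol*

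**What the plan says.** **Replacement.** Protocol Section 7.3 says of participants who leave early that "they may be replaced at the discretion of the Medical Monitor in consultation with the Principal Investigator". It then gives the allocation rule: "In Parts B and C participants will be assigned to same treatment as the participant prematurely discontinued". The synopsis (Brief Summary) adds one word: "In Parts B and C participants will be assigned to same treatment as the last participant prematurely discontinued". Both versions carry over the treatment and nothing else.

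**Blinding.** Section 6.3 blinds participants and site staff and leaves the site pharmacy unblinded. It also says: "A participant will be withdrawn if the participant's treatment code is unblinded by the Investigator or treating physician".

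**Part C strata.** Section 4.1 says: "Randomisation will be stratified to ensure 6 participants using intermittent SABA or intermittent ICS/LABA and 6 participants taking regular ICS or ICS/LABA" are to be on active treatment. Inclusion criterion 5 (Section 5.1.2) sets recruitment at 8 and 8, and SAP Section 1.2 gives 6 active and 2 placebo in each stratum.

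No visible section says how a replacement is allocated after a code-break, or that a Part C replacement must come from the stratum of the participant who left.

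**The concern.** Each rule is ordinary on its own. Mandatory withdrawal after a code-break limits the consequences of unblinding, and copying the treatment keeps the arm sizes at plan. Together they pass the revealed allocation on to a new participant. The person who learned it may be the one who assesses that new participant.

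Investigator judgement matters here. SAP Section 4.2.1 defines a drug-related event by the investigator's classification. The dose-escalation stopping criteria (Protocol Section 6.5.2) and the study stopping criteria (Section 7.2.1) both depend on events judged at least possibly related. The Principal Investigator or a delegate also sits on the Dose Escalation Committee (Section 10.1.5.1), which reviews Part B data before Part C is dosed. Knowing the allocation could move a relatedness call in either direction.

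**Working it through.** **1. The plan's own figures.**
- Allocation: 16 × 3/4 = 12 active and 4 placebo in each of Parts B and C; 8 × 3/4 = 6 active and 2 placebo per Part C stratum. These match the documents.
- Chance of seeing no event among 12 active (Protocol Section 9.2): (1 − 0.05)^12 = 0.540 and (1 − 0.20)^12 = 0.069, against the stated 54% and 7%. Reproduced.

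**2. The blinding chain.**
- The Investigator breaks a code, so the participant is withdrawn (Section 6.3).
- The Medical Monitor, consulting the Principal Investigator, may replace that participant (Section 7.3).
- The replacement receives the same treatment (Section 7.3).
- For an investigator who saw the code and knows whose place is being filled, the probability that the replacement is on active goes from 12/16 = 75% to 100% or 0%.

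**3. How far it reaches.**
- One replacement among planned completers: 1/12 = 8.3% of active, or 1/4 = 25% of placebo, in that part.
- In the Safety set the withdrawn participant stays in if already dosed, so the shares are 1/13 = 7.7% or 1/5 = 20%.
- Other participants' allocations are not revealed.
- These shares are conditional on the event. The documents give no code-break rate, so no expected effect can be calculated.

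**4. The word *last* in the synopsis.** Suppose one active and one placebo participant leave before either is replaced: 12:4 becomes 11:3. Section 7.3 restores 12:4. The synopsis, read literally, gives both replacements the treatment of whoever left last: 13:3 or 11:5.

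**5. The stratum gap in Part C (active:placebo).**

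| Case | Stratum 1 | Stratum 2 |
|---|---|---|
| Plan | 6:2 | 6:2 |
| One active participant from stratum 1 replaced from stratum 2, completers | 5:2 | 7:2 |
| Same case, dosed (Safety set) | 6:2 | 7:2 |
| Active vacancy in stratum 1 and placebo vacancy in stratum 2, filled crosswise, completers | 5:3 | 7:1 |

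The second row leaves 7 and 9 completers, which does not fit the 8 and 8 quota if that quota governs filled places. The last row keeps 8 and 8, but it needs two vacancies in opposite arms and different strata.

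**6. Use of stratum in the analysis.** SAP Section 4.3 analyses Part C pharmacokinetics as one cohort, and the accumulation model in SAP Section 4.3.2.2 has only day and subject. No visible SAP summary or model uses stratum.

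**The case against.** A reader might infer that the rule can undo both the stratification and the blind. The documents do not support that.

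*Stratification.* Section 4.1 says that randomisation is stratified, and a later replacement does not reverse it. Completer numbers are an aim, stated by arm and not by stratum. The 8 and 8 quota would largely prevent a single cross-stratum replacement. The primary endpoint uses the Safety set, which keeps a dosed participant who withdraws, and no hypothesis is tested. The randomisation schedule is not public and may already reserve replacement numbers by stratum. All this stands; what remains is a missing phrase in the rule.

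*The word* last. The literal reading defeats the 12 active and 4 placebo target given in the same synopsis section. The Part A sentence uses the same phrase for the person whose sequence is taken over, so it most naturally means the person being replaced. This stands: the mismatch is editorial.

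*Blind.* The leak needs a code-break, a discretionary decision to replace, and an investigator who knows which vacancy is being filled. The person who broke the code need not be the Principal Investigator who is consulted. Section 7.3 expects withdrawals to be uncommon and already allows no replacement. If the code-break followed a possibly related serious event, Section 6.5.2 halts dosing at that level and Section 7.2.1 pauses the study, so a same-dose replacement would not simply go ahead. These points make the event rare but do not remove it. Codes can be broken for other reasons, and when a replacement is made the written rule requires the known treatment to be copied.

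**Conclusion.** The point holds as a narrow gap in masking that is cheap to close. In Parts B and C, following Sections 6.3 and 7.3 as written can produce a replacement whose allocation is known to an investigator who judges relatedness. It affects one replacement per such event: 1/12 of planned active or 1/4 of planned placebo in that part.

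This assumes that the Medical Monitor chooses to replace, that the investigator who saw the code knows whose place is being filled, and that the same investigator assesses the replacement. It does not unblind the cohort and changes no sample-size figure.

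The stratum wording and the synopsis mismatch are minor. A cross-stratum active replacement would leave 5 and 7 active completers (6 and 7 active dosed) instead of 6 and 6, and no visible SAP analysis depends on it.

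**What to change.** **Main change**, in Section 7.3 and the synopsis: state that when the site has broken a participant's code, the treatment is not copied to a replacement. Either do not replace, or allocate the replacement from a reserve 3:1 list, stratified in Part C, held by the already unblinded site pharmacy.

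**Wording to align in the same edit:**
- Use the Section 7.3 text in the synopsis, without *last*.
- State that a Part C replacement comes from the same asthma stratum as the participant who left.

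**Cost.** A few sentences and a short reserve list. After a code-break in the active arm, completers may finish at 11:5 (replacement drawn to placebo) or 11:4 (not replaced). After one in the placebo arm, they may finish at 13:3 or 12:3. With no formal hypothesis, departing from 12:4 by one participant is a small price for keeping the replacement's assessor masked. The same 13:3 and 11:5 splits arise under the literal synopsis wording, but there they bring no gain in masking.
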